6.10.1 Adverse Events

Adverse events will be coded using the Medical Dictionary for Regulatory Activities (MedDRA) Version 20.1 or higher and graded by the investigator using the CTCAE v5.0 or the current version. All adverse events (AEs) will be classified as either pre-treatment AEs or treatment-emergent AEs (TEAEs) as follows:

- Pre-treatment AEs are events that start prior to the date of first dose of study treatment that do not qualify to be treatment-emergent as per the definition below.
- TEAEs are events with start date on or after the first dose of study treatment or events that started prior to the first dose of study treatment whose severity worsened on or after the first dose of study treatment. All adverse events considered by the investigator as at least possibly related to the study treatment will be considered as treatment-emergent irrespective of the start date.

Subject incidence of treatment-emergent TEAEs, treatment-emergent serious AEs (TESAEs), DLT AEs, TEAEs leading to treatment discontinuation and TEAEs with an outcome of death will be summarized by SOC and PT. These Adverse events will also be further summarized by worst severity grade and relationship to study treatment.

TEAEs of special interest (TEAESIs) will also be summarized by SOC, PT, and worst severity grade.

All AE data will be listed for each cohort. Treatment-emergence status will be flagged in the listing. In addition, listings of serious AEs (SAEs), AEs leading to discontinuation of study treatment and AEs resulting in death will be produced.

Statistical Analysis Plan

Sponsor Name: Equillium Inc.

Sponsor Protocol ID: EQ001-aGVHD-001

The severity of all AEs is recorded as mild, moderate, or severe. The relationship between an AE and study treatment is assessed as Not Related, Unlikely Related, Possibly, Probably, Related by the investigator. A study treatment-related AE is an AE considered by the investigator as one that is at least 'possibly related' to study treatment or with unknown/missing relationship to study treatment.

An overview table will summarize the number and percentage of subjects with at least one of the following TEAEs, where subjects with more than one TEAE in a particular category are counted only once in that category:

- Any TEAE
- Any DLT AE

- Any TEAE by severity (mild, moderate, severe)
- Any TEAE related to study treatment
- Any Grade 3 or higher TEAE
- Any TEAE leading to study treatment discontinuation
- Any TEAE leading to discontinuation from the study
- Any TEAE with an outcome of death
- Any TESAE
- Any TESAE related to study treatment
- Any TESAE with an outcome of death
- Any TESAE related to study treatment with an outcome of death
- Any TESAE leading to treatment discontinuation
- Any TESAE leading to discontinuation from the study

The number and percentage of subjects reporting TEAEs will be summarized by SOC and PT. Tables will be sorted by the descending order of incidence in overall total column with respect to SOC first and descending order of incidence with respect to PT within SOC. The following summaries will be produced:

- TEAEs by SOC and PT
- DLT AEs by SOC and PT
- TEAEs related to study treatment by SOC and PT
- TEAEs by worst severity grade by SOC and PT
- TEAEs leading to the discontinuation of study treatment by SOC and PT
- TESAEs by SOC and PT
- TESAEs related to study treatment by SOC and PT
- TEAEs with an outcome of death by SOC and PT

Statistical Analysis Plan

Sponsor Name: Equillium Inc.

Sponsor Protocol ID: EQ001-aGVHD-001

- TESAEs with an outcome of death by SOC and PT

In the above summaries, subjects with more than one AE within a particular SOC are counted only once for that SOC. Similarly, subjects with more than one AE within a particular PT are counted only once for that PT. For summaries by worst severity grade, subjects with multiple AEs within a particular SOC or PT will be counted under the worst severity grade within that SOC or PT.

6.10.2 Laboratory Evaluations

Clinical laboratory data will be collected using local labs and thus normal ranges may differ from lab to lab making head-to-head comparison of laboratory values or their changes across labs not very meaningful. Therefore, data including changes from baseline will not be summarized by assessment visit. All laboratory parameters that can be graded using the CTCAE will be graded; these include all scheduled and unscheduled laboratory data. For selected parameters, following summaries will be produced:

- Worst post-baseline severity grade
- Shift summary of baseline grade to worst post-baseline severity grade.

In addition, for selected parameters (ALT, AST, Total Bilirubin, ALP, GGT and LDH), number and percentage of subjects with worsening grade shifts (1 grade increase, 2 grades increase, and 3 or more grades increase) from baseline to worst post-baseline grade will be summarized. For the above parameters, time to earliest grade increase will also be summarized using the KM method. For subjects not showing any grade increase, time to earliest grade increase will be considered censored at the last known laboratory assessment visit.

6.10.3 Vital Signs

[figure not shown]
Vital signs data and their changes from baseline will be summarized by nominal assessment visits and worst post-baseline using standard descriptive statistics. For these by-visit summaries, only data from scheduled visits will be included.

Statistical Analysis Plan

Sponsor Name: Equillium Inc.

Sponsor Protocol ID: EQ001-aGVHD-001

Number and percentage of subjects showing each of the following vital sign abnormalities at any post-baseline assessment (including unscheduled assessments) will be summarized:

6.10.4 **Electrocardiograms**

The following quantitative ECG measurements will be listed and summarized by nominal assessment visits and worst post-baseline using standard descriptive statistics:

- Heart rate (bpm)
- RR interval (msec)
- PR interval (msec)
- QRS interval (msec)
- QT interval (msec)
- QTcF interval (msec) (calculated using QT and Heart rate or RR interval)

Where QTcF denotes the QT corrected for heart rate calculated using the Fridericia's formula:

$$QTcF = 10 \times QT / (RR)^{1/3}$$

Worst post-baseline overall interpretation of ECGs ('normal', 'abnormal, not clinically significant', 'abnormal, clinically significant') across all available post-baseline ECG data including any unscheduled assessments will be summarized in the frequency and percent format. Further, a categorical summary of baseline QTcF and of worst (highest) post-baseline QTcF result (msec) will be summarized for the categories defined below:

- ≤ 450

Statistical Analysis Plan

Sponsor Name: Equillium Inc.

Sponsor Protocol ID: EQ001-aGVHD-001

- >450-≤480
- >480-≤500
- >500

In addition, worst QTcF increase from baseline will also be summarized for the following categorical increases:

- ≤30
- >30-≤60
- >60

6.10.5 Relapse of Underlying Malignancy and Death

Number and percentage of subjects whose underlying malignancy relapsed or died will be summarized for the following categories:

- Malignancy relapsed by Day 29
- Death by Day 29
- Death by Day 29 with no relapse of malignancy
- Malignancy relapsed during the study
- Death during study with no relapse of malignancy
- Death during study after relapse of malignancy

6.10.6 Physical Examination

Abnormalities identified from physical examination are recorded in the eCRF will be listed.

6.10.7 Anti-Drug Antibody (ADA) and Neutralizing ADA (NAB)

Serum samples collected for detection of ADA against EQ001 will be batched and run at the end of Part A unless a subject has a suspected hypersensitivity reaction, the samples collected for that subject will be analyzed in real time. If data are available, ADA and NAB data will be summarized by visit further broken down the confirmed positive results by titer level.

7. Topline Results

When the last subject in last cohort in Part A completes Day 29 visit (data cut-off date), data from all Part A cohorts may be summarized to release topline results. For this analysis, all the assessments done on or prior to the data cut-off date will be entered and cleaned prior to data summarization. A selected set of summary tables, figures and listings will be produced. These may include but not limited to:

- Subject Disposition

Statistical Analysis Plan

Sponsor Name: Equillium Inc.

Sponsor Protocol ID: EQ001-aGVHD-001

- Demographic and Baseline Characteristics
- Baseline Disease and Graft Characteristics
- Exposure to EQ001
- Response to Therapy by Assessment Day
- aGVHD Activity Index Score and Changes from Baseline by Assessment Day
- Overall Summary of Treatment-Emergent Adverse Events
- Treatment-emergent adverse events by System Organ Class and Preferred Term
- Line Plot of Absolute Lymphocyte Counts Over Time by Subject – Cohort 1
- Line Plot of Absolute Lymphocyte Counts Over Time by Subject – Cohort 2
- Bar Graph of Response Rates at Day 29 – Cohort 1
- Bar Graph of Response Rates at Day 29 – Cohort 2

8. Changes in Planned Analysis

None

Statistical Analysis Plan

Sponsor Name: Equillium Inc.

Sponsor Protocol ID: EQ001-aGVHD-001

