Subjects will be considered evaluable for DLT assessment if they have received at least two doses of study drug and completed through Study Day 29 assessments or received at least one dose of study drug and had a DLT within the DLT window. During the DLT assessment window, subjects who do not complete the specified study procedures or withdraw from the study for reasons other than a DLT may be replaced. Replaced subjects will receive the same dose level and cohort assignment as the subject they are replacing.

Established Data and Safety Monitoring Committee (DSMC) will apply the following dose escalation rules based on the subject incidence of DLTs:

- If 0 of the 3 initial evaluable subjects experiences a DLT, then escalation may proceed to the next highest dose level.

[figure not shown]
Statistical Analysis Plan

Sponsor Name: Equillium Inc.

Sponsor Protocol ID: EQ001-aGVHD-001

- If 1 of the 3 initial evaluable subjects experiences a DLT, then 3 additional subjects will be enrolled at the same dose level for a total of up to 6 evaluable subjects.
 - If 1 out of the 6 subjects experience a DLT, then escalation may proceed to the next higher dose level.
 - If 2 or more out of the 6 subjects experience a DLT, escalation to the next dose level will not proceed, next lower dose level will enroll additional subjects for a total of 6 evaluable subjects.
- If 2 of the 3 initial evaluable subjects experience DLTs, escalation to the next dose level will not proceed, next lower dose level will enroll additional subjects for a total of 6 evaluable subjects.

Enrollment of the next higher dose cohort will not commence until all safety data from all subjects from prior cohorts and all available safety data from the current cohort through Study Day 29 have been reviewed by the DSMC and approval is granted for dose escalation.

3. Clinical Activity and Safety Variables for Part A

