6.10 Safety

All safety data summaries will use the safety population. Safety analyses will be presented by cohort and overall unless otherwise specified.

Number and percent of subjects experiencing any DLTs will be presented by cohort. A listing of DLTs will also be provided.

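### Topline by-cohort TEAE percentages in Part A would compare unequal follow-up, generally shorter at higher doses, because SAP Section 7 applies one calendar cut and uses all data up to it

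*SAP*

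**What the plan says.** The point comes from reading five parts of the SAP together.

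- **Cut-off (Section 7, Topline Results).** The trigger is "When the last subject in last cohort in Part A completes Day 29 visit (data cut-off date), data from all Part A cohorts" may be summarised for release. The data are not truncated at each subject's own Day 29: "all the assessments done on or prior to the data cut-off date will be entered and cleaned prior to data summarization".
- **Outputs (Section 7).** The list of possible outputs includes "Overall Summary of Treatment-Emergent Adverse Events" and a table of TEAEs by SOC and PT.
- **Sequential enrolment (Section 2.2).** "Enrollment of the next higher dose cohort will not commence until all safety data from all subjects from prior cohorts", together with "all available safety data from the current cohort through Study Day 29 have been reviewed by the DSMC and approval is granted" for escalation.
- **TEAE definition (Section 6.10.1).** "TEAEs are events with start date on or after the first dose of study treatment", or earlier events that worsen after it. The visible text gives no upper time limit.
- **Display (Sections 6.10 and 6.10.1).** "Safety analyses will be presented by cohort and overall unless otherwise specified". The measure is a crude proportion: "The number and percentage of subjects reporting TEAEs will be summarized by SOC and PT". No exposure-adjusted rate appears. The exposure summary in Section 6.6 counts doses, not days of follow-up.

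Protocol Section 7 runs AE collection to Day 169 for subjects who complete study drug, and to Day 85 for those who stop it early.

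**The concern.** Dose is tied to calendar time by design. Each higher dose level starts only after the level below has been followed to Day 29 and reviewed. A single calendar cut therefore gives the lower doses longer follow-up, and a crude percentage of subjects with at least one event can only rise with follow-up. A topline TEAE table by cohort could show falling incidence with rising dose when the true risk is the same, or hide a real increase.

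Finding optimal dose levels is a primary objective of Part A. Protocol Section 3.2 allows further safety and tolerability data to be weighed if more than one dose meets the criteria. Released tables with this built-in tilt would be easy to misread in that setting.

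**Working it through.** The documents state no follow-up length at the topline cut, so there is no figure of theirs to reproduce. The schedule itself is consistent: five doses every 14 days fall on Days 1, 15, 29, 43 and 57, and Protocol Section 7 also places the end of dosing at Day 57.

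**Step 1: follow-up at the cut.** Day 29 is 28 days after Day 1, so consecutive cohorts start at least 28 days apart. Let K be the number of dose cohorts enrolled, k the cohort, and g the days between Day 29 of one cohort and the first dose of the next. The last subject of cohort k is then at study day 29 + (28 + g) × (K − k), or later. With g = 0 and no accrual time:

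| Cohorts enrolled | Cohort 1 | Cohort 2 | Cohort 3 | Cohort 4 |
|---|---|---|---|---|
| 2 | 57 | 29 | – | – |
| 3 | 85 | 57 | 29 | – |
| 4 | 113 | 85 | 57 | 29 |

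For four cohorts, 29 + 3 × 28 = 113, and 113/29 = 3.9. A 14-day review gap gives Cohort 1 29 + 3 × 42 = 155. A 28-day gap gives 29 + 3 × 56 = 197, which the collection limit caps at 169 for completers. For early discontinuers the cap is 85. At the cut, the last subject of the top cohort has reached only the third dose visit, while completers in every other cohort have had all five doses.

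**Step 2: effect on crude incidence.** Assume the same 29-day risk p at every dose. The documents give no value, so p = 30% is an illustration. Under constant hazard, incidence by day d is 1 − (1 − p)^(d/29):

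- Day 29: 30%
- Day 57: 1 − 0.7^(57/29) = 50%
- Day 85: 1 − 0.7^(85/29) = 65%
- Day 113: 1 − 0.7^(113/29) = 75%

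The result depends on when first events happen. For the lowest of four cohorts, against 30% in the highest:

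| When first events occur | Lowest cohort |
|---|---|
| All within 29 days | 30% |
| Constant hazard, ending at Day 57 | about 50% |
| Constant hazard to Day 113 | about 75% |

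Under constant hazard, p = 10% becomes 34% by Day 113, and p = 50% becomes 93%.

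**Step 3: chance of a misleading ordering.** Take 6 subjects per cohort, p = 30% and constant hazard. With X ~ Binomial(6, 0.751) in the lowest cohort and Y ~ Binomial(6, 0.30) in the highest, P(X > Y) = 92%. With equal follow-up, both at 0.30, it is 38%. With 3 per cohort the figures are 79% and 33%. These are the upper end of the range, because they use four cohorts and constant hazard.

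**Step 4: after the change.** Counting only events with onset on Days 1-29 gives every cohort the same nominal window. With equal true risk, the expected percentages are then equal (30% and 30%).

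**The case against.** A reader might infer that the topline necessarily compares 29 days at the highest dose with at least 113 days at the lowest, and so biases dose selection toward the highest dose. The documents do not support that, for these reasons:

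- **Number of cohorts.** Protocol Section 3.2 stops escalation once a second dose level meets the optimal-dose criteria, so two or three cohorts are possible. The floor of 113 days needs four.
- **Individual follow-up.** AE collection ends at Day 85 for early discontinuers, and deaths and withdrawals shorten it further. Day 29 is exact only for the last subject. If Cohort 4 grows from 3 to 6 after a DLT, its first three subjects are at about Day 57 or later.
- **Which cohort is last.** After two or more DLTs a lower dose is refilled, and up to about 15 further subjects join at the selected dose. If either group supplies the last subject, the gradient by dose can flatten or change.
- **Role of the tables.** The topline is optional and interim. Escalation rests on DLTs in a fixed Day 1-29 window, and no passage says that topline TEAE tables select the dose. Final Part A tables would have fuller follow-up.
- **Size.** Dosing ends at Day 57, and infusion-related reactions, one of the reactions the protocol expects, are tied to dosing. Constant hazard to Day 113 is therefore near the worst case.
- **Missing text.** The public SAP goes from Section 4.3 to Section 6, so a windowing rule in the unseen part cannot be excluded.

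All of this stands as a limit on size and consequence. It does not remove the mechanism: even two cohorts give 57 versus 29 days. The topline list does include exposure to EQ001, but dose counts do not let a reader correct for follow-up time.

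A reader might also infer that the topline leaves out Cohorts 3 and 4, because some listed figures name only Cohorts 1 and 2. The list is expressly not exhaustive, so that does not follow.

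**Conclusion.** The point holds in a limited form. On the visible text, a topline by-cohort TEAE table would compare unequal follow-up, generally shorter at higher doses. With no review or accrual time, the lowest and highest cohorts are at Day 57 versus 29, 85 versus 29 or 113 versus 29 for two, three or four cohorts, within the Day 169 and Day 85 collection limits.

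The resulting distortion runs from none, if all first events fall within 29 days, to about 75% versus 30% with four cohorts under equal constant hazard and an assumed 30% 29-day risk. The direction assumes that the last subject belongs to the highest dose.

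The effect is confined to the optional interim tables. DLT summaries and Day 29 response already use a common time point. Severity is minor to moderate: worth correcting because it is cheap, but not a condition for proceeding.

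**What to change.** In SAP Section 7:

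1. Add by-cohort topline tables of TEAEs, TESAEs and Grade 3 or higher TEAEs, limited to onset on Study Days 1-29.
2. Keep the all-data tables beside them, and give subject-days of follow-up and events per 100 subject-days for each cohort.

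The Day 1-29 tables make the between-cohort comparison fair, and the all-data tables keep later events visible. The rates adjust fully for unequal follow-up only if the hazard is roughly constant, so they support the windowed tables and do not replace them. By-visit response displays need no restriction.

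The cost is SAP wording and a few extra outputs, with no new data collection. The Day 1-29 tables will contain fewer events. If the unseen SAP text already has such a window, a cross-reference in Section 7 is enough for the first item.
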